#### 6.14.1 Early Removal of RBP-6000

In the event of an emergency or if a subject withdraws or is withdrawn within the first 14 days of receiving an injection of RBP-6000, subjects may have the option to have the depot surgically removed by a physician delegated to perform surgery. The medically responsible physician should carefully discuss this option with subjects given the use of ATRIGEL Delivery System and the feasibility of extracting the depot. The surgical procedure requires a small incision in the abdomen where the depot was placed, removal of the depot with forceps, and suturing to close the incision. The subject should have the EOS assessments performed at the time of early removal of RBP-6000. Subjects that have had an RBP-6000 depot removed should have follow-up telephone contact(s) within 7 to 14 days to assess status and for resolution of related AEs. In the event a subject cannot be contacted for the follow-up telephone contact, a minimum of 2 documented telephone calls followed by a certified mailed letter is considered reasonable. At this point, the subject may be considered lost to follow-up.

The extracted RBP-6000 depot will be disposed of into an appropriate, secure biohazard container per the standard operating procedures (SOPs) at the study site.

Detailed RBP-6000 depot removal instructions are in [Appendix 8](#).

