The suicidal ideation intensity rating is the sum of the five intensity item scores to create a total score (range 0 to 25). The five intensity items include frequency, duration, controllability, deterrents, and reason for ideation. Each item is scored from 0 to 5 with 5 representing the most severe intensity.

Suicidal Behavior Scoring

The suicidal ideation score ranges from 0 to 5 and depends on the answers to the suicidal behavior portion of the eC-SSRS. The score is the maximum suicidal ideation category (in the following order: 1 = preparatory acts or behavior, 2 = aborted attempt, 3 = interrupted attempt, 4 = actual attempt, and 5 if the subject has an AE with a preferred term of completed suicide. If all answers to these questions are "No" and the subject does not have an AE with a preferred term of completed suicide then the suicidal behavior score is 0.

Treatment Duration (weeks)

Treatment duration will be defined as $(\text{treatment stop date} - \text{treatment start date} + 1)/7$ where treatment stop date is defined as date of last RBP-6000 injection + 28 days.

Sponsor: Indivior Inc.
 Protocol no: RB-US-13-0003

Percentage of Urine Drug Screen and Self-Report Results

Subjects' self-reported illicit drug use from the TLFB and results from the UDS will be combined into a single endpoint in the following manner:

- If both the TLFB and the UDS have a negative result at a particular visit, then the visit will be considered to have a negative result at that visit.
- If either the TLFB or UDS, or both, have a non-negative result at a particular visit, then the visit will be considered to have a non-negative result at that visit.
- To be conservative, missing UDS or TLFB data will be imputed as non-negative.

Urine Drug Screen Result for Opioids	Self-Report of Illicit Opioid Use Result	Overall Result
Nonnegative	Nonnegative	Nonnegative
Nonnegative	Negative	Nonnegative
Negative	Nonnegative	Nonnegative
Negative	Negative	Negative

Treatment Success

A subject is defined as a treatment success if $\geq 80\%$ urine samples negative combined with self-reports negative.

Visit Window for Remapping of Early Termination visit

Duration will be derived in days as (ET visit date – treatment start date) + 1.

Sponsor: Indivior Inc.
 Protocol no: RB-US-13-0003

Visit window for safety and efficacy assessments.

Study Visit	Lower Window for Analysis Day (ADY)	Upper Window for ADY
Week 1 Day 1	1	1
Week 1 Day 2	2	5
Week 2 Day 8	6	12
Week 3 Day 15	13	19

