6.3 Safety Analysis Set

The Safety Analysis Set comprises all subjects who received at least 1 dose of RBP-6000 during the open-label treatment period of the study. This analysis set will be used for all safety analyses.

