9.4 Study Treatment Exposure

A summary of the exposure to SUBOXONE during the Run-In period will be summarized by Run-In period (induction/dose adjustment), visit, administration/dispensation, and dosage for the Run-In Safety Analysis Set. A listing of SUBOXONE exposure (administration/dispensation) will be provided.

Exposure will be derived as date of first RBP-6000 injection on the RB-US-13-0003 study, to 28 days after the last RBP-6000 injection on this study.

The duration of exposure in the 0-<4 weeks through 48 – <52 weeks, total number of RBP-6000 doses received, the total number of actual doses as a continuous summary, and the total number of actual doses as a categorical summary will be presented for the Safety Analysis Set. RBP-6000 exposure data will also be listed detailing the dose of RBP-6000 received at each injection and the number of days between injections.

The number of subjects who have early removal of the RBP-6000 depot by physician will be presented for the Safety Analysis Set. Early removal of the study drug depot data including the reason and removal date and time will be listed.

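### The exposure rule always adds 28 days after the last injection, even when the depot is removed or the subject dies sooner, so the planned 0 to <4 weeks category cannot contain anyone

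*SAP*

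**What the plan says.** SAP section 5.0 computes treatment duration in weeks as stop date minus start date plus one day, divided by 7, where "treatment stop date is defined as date of last RBP-6000 injection + 28 days". Section 9.4 derives exposure from the first injection "to 28 days after the last RBP-6000 injection on this study", with no extra day written. For the exposure table, section 9.4 plans "The duration of exposure in the 0-<4 weeks through" a last category of 48 to <52 weeks. The table is for the Safety Analysis Set, and section 6.3 states: "The Safety Analysis Set comprises all subjects who received at least 1 dose of RBP-6000 during the open-label treatment period of the study".

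Protocol section 6.14.1 provides for surgical removal of the depot in an emergency or "if a subject withdraws or is withdrawn within the first 14 days of receiving an injection of RBP-6000". The SAP expects such cases. Section 9.4 says: "The number of subjects who have early removal of the RBP-6000 depot by physician will be presented for the Safety Analysis Set", and it lists the reason, date and time of each removal. Deaths are defined in section 5.0 and tabulated and listed under section 9.6.1.4. Neither event is linked to the stop date.

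**The concern.** The lowest exposure category exists to show how many subjects had less than one dosing interval of treatment. If the definition makes that impossible, the table reports a zero that a reader will take as a result when it is only a consequence of the formula. The subjects who ought to be there, those whose only depot was taken out or who died within four weeks, are also the ones for whom a safety reader most wants accurate exposure. Long-term safety is the primary objective, so the exposure table is a main display and should not contain a cell that is fixed in advance.

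**Working it through.** **Inputs.** Stop date = last injection + 28 days (SAP 5.0 and 9.4). Inclusive + 1 day (SAP 5.0 only). At least one injection (SAP 6.3). Nominal spacing of 28 days (Protocol 5.3). Removal within 14 days of an injection (Protocol 6.14.1). Planned treatment periods of 48 weeks for 12 injections and 24 weeks for 6 (SAP 3.3).

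**Formula.** For k injections at 28-day spacing, SAP 5.0 gives [28(k − 1) + 28 + 1]/7 weeks.

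**The plan's own figures.**
- k = 12: (308 + 29)/7 = 337/7 = 48.14 weeks, or 336/7 = 48.00 without the + 1. The plan says 48.
- k = 6: (140 + 29)/7 = 169/7 = 24.14 weeks, or 168/7 = 24.00 without the + 1. The plan says 24.

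The rule reproduces the planned periods. The day totals 337 and 169 are the end-of-study days in Protocol Appendices 5 and 3.

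**Minimum possible duration (k = 1).**
- SAP 5.0: 29/7 = 4.14 weeks.
- SAP 9.4 wording: 28/7 = 4.00 weeks.

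Neither is below 4, so the 0 to <4 weeks category is empty on either reading.

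**Excess for an event d days after the last injection (d ≤ 28).** With inclusive counting, time from the last injection to the event is d + 1 days. The SAP credits 29, so the excess is 28 − d days. The table shows a single-injection subject.

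| d | Days to event | Weeks | Days credited by SAP 5.0 | Excess (days) |
|---|---|---|---|---|
| 0 | 1 | 0.14 | 29 | 28 |
| 7 | 8 | 1.14 | 29 | 21 |
| 14 | 15 | 2.14 | 29 | 14 |
| 26 | 27 | 3.86 | 29 | 2 |

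A removal within the 14-day window is thus over-credited by 14 to 28 days. A death can fall anywhere in the interval.

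**Relative size, removal at d = 14, 28-day spacing.**
- 1 injection: 14/15 = 93%.
- 6 injections: 14/(140 + 15) = 14/155 = 9.0%.
- 12 injections: 14/(308 + 15) = 14/323 = 4.3%.

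**The case against.** For a subject who keeps the depot, the 28-day credit is reasonable. Protocol section 5.2.3 describes release over about 28 days, and section 1.4.2 reports mean terminal half-lives of 1078 to 1573 hours, so drug remains after that. The + 1 is ordinary inclusive counting. Removals are already counted and listed with date and time, deaths are tabulated and listed, and section 9.4 also summarizes the number of doses, so an attentive reader can find every affected subject. Removal does not clear drug already absorbed. All of this stands, and it limits the point to subjects with early removal or death.

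A reader might infer more, but the documents do not support it:
- *That exposure is overstated for everyone, and the stop date should be last injection + 27 days.* Apart from the one inclusive day, retained depots are credited as the protocol describes. The change would also make category boundaries more fragile. A nominal k-injection subject now has 28k + 1 days and stays in category if net one day early; with + 27 the subject would have exactly 28k days and would drop a category.
- *That visit windows misclassify subjects with equal dosing.* A subject treated at shorter intervals does have a shorter duration, and any cut-point separates neighbors. The planned dose-count summary already shows number of injections.
- *That adverse event results or the 100-subject one-year target are affected.* Adverse events are reported as percentages of subjects (SAP 9.6.1.1), and the treatment-emergent definition has its own limit of 30 days after the last dose (SAP 5.0). Nothing in the documents shows that removals or deaths would alter the one-year count.

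None of this makes the lowest category reachable or supplies the missing truncation.

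**Conclusion.** The point holds for a limited group. As written, the rule gives a wrong exposure figure for any subject whose last depot is removed, or who dies, before 28 days have passed since the last injection, and it makes the lowest planned category empty by construction. The empty category needs no assumption beyond the SAP's own definitions. The overstatement is at most 28 days per affected subject: nearly double for a single-injection subject with removal at 14 days, about 9% after 6 injections and about 4% after 12. These figures treat the removal date as the end of exposure from the last depot and assume 28-day spacing. The documents do not give the numbers of removals and deaths, so no aggregate effect can be computed, and it may be small. The change is worth making because it is cheap and corrects a table central to the primary objective.

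**What to change.** In SAP sections 5.0 and 9.4, define the treatment stop date as the earliest of last injection + 28 days, date of removal of the last depot, and date of death. Use the same day-count, with or without the + 1, in both sections. Dropping the + 1 alone would not help, since the minimum would still be 4.00 weeks. With the truncation, a single-injection subject with removal 14 days after injection has 15 days (2.14 weeks), or 14 days (2.00 weeks) without the + 1, and falls in the lowest category.

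The cost is one definition and a re-run of the exposure table. Removal dates are already to be listed. The SAP lists deaths without naming a date field, so its availability should be confirmed. Reported exposure will fall slightly for the affected subjects. After several injections the removal date marks the end of the last depot, not of all buprenorphine exposure, and a table footnote should say so.

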6.0 Analysis Sets

6.1 All Screened Subjects

All screened subjects include any subject who signed the informed consent form.

Sponsor: Indivior Inc.
Protocol no: RB-US-13-0003

6.2 Run-In Safety Analysis Set

The Run-In Safety Analysis Set will include all subjects who received at least 1 dose of SUBOXONE during the Run-In period of the study.

6.3 Safety Analysis Set

The Safety Analysis Set comprises all subjects who received at least 1 dose of RBP-6000 during the open-label treatment period of the study. This analysis set will be used for all safety analyses.

6.4 PK Analysis Set

The PK Analysis Set will include any subject who receives a dose of RBP-6000 or at least 1 dose of SUBOXONE sublingual film and has at least 1 PK sample collected post-dose.

7.0 Interim Analyses (Data Cut Review)

An interim safety analysis was conducted using all data up to and including the 12th August 2016. The data was analysed and reported as per SAP version 2.0.

8.0 Data Review

8.1 Data Handling and Transfer

All of the data will come from the PRA Health Sciences data management group in SAS® dataset format (SAS version 9.4 or later) converted to Study Data Tabulation Model (SDTM) using SDTM Implementation Guide (SDTMIG) Version 3.1.3. Please refer to the Data Quality Plan for details.

The following vendors will be providing data for the study:

- WCT: PK data;
- ACM: Central laboratory data;
- ERT: SOWS, COWS, Opioid Craving VAS, Injection site grading scale, TLFB results, injection pain VAS, end time of the injections, and eC-SSRS data;
- Cardiocore: ECG data.

8.2 Data Screening

Beyond the data screening built into the Data Management Plan, the programming of analysis datasets, tables, figures, and listings (TFLs) provides additional data screening. Presumed data issues will be output into SAS logs identified by the word "Problem" and extracted from the logs by a SAS macro and sent to PRA Data Management.

Review of a pre-data cut subset TFL run allows for further data screening prior to lock. The pre-data cut subset TFLs will be discussed with the sponsor in a data review meeting to identify any final data issues and seek corrections prior to database lock for the interim lock and final lock. The PRA statistician and the sponsor must approve final database lock.

9.0 Statistical Methods

All statistical analyses will be performed using SAS® Version 9.4 or higher.

Categorical variables will be summarized using counts and percentages. Percentages will be rounded to one decimal place; except 100% will be displayed without any decimal places and percentages will not be displayed for zero counts. When assessments are not applicable (ie Post injection 6 visits for roll-over subjects), an N/A will displayed instead of a zero,

Sponsor: Indivior Inc.
Protocol no: RB-US-13-0003

Continuous variables will be summarized using the number of observations (n), mean, standard deviation (SD), median, minimum, and maximum. The minimum, maximum, and 95% CI values (in some instances) will be displayed to the same level of precision as the raw data, the median and mean to one additional decimal place and the SD to two additional decimal places. The maximum number of decimal places will be 4. All summaries will be presented by subject type (de novo or roll-over) unless otherwise stated.

Unless otherwise stated, summaries will be presented by subject type (de novo or roll-over and total). Missing values will be presented by blank spaces. For partially missing dates, the information present will be printed; e.g., "--JAN2000".

For dichotomous outcome measures such as urine drug screen results (negative; non-negative) and self-reports for illicit opioid use (negative; non-negative), any missing observation will be set equal to "non-negative." Missing results for substances other than opioids will not be imputed. For all continuous endpoints (e.g., COWS, SOWS, and VAS), the missing data will not be imputed.

Only scheduled assessments per protocol Amendment 4 will be presented in tables and figures except for worst case post-baseline and at any time types of analyses (all post-baseline including unscheduled assessments data will be considered for this derivation) but all data will be presented in the listings.

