## 6.8 Administration of Study Drug

The study drug will be assigned by an IWRS system. Injections will be administered by a physician or suitably-qualified designee (e.g., physician, nurse, nurse practitioner, PA) who has been delegated to perform the task. Study drug will be supplied only to subjects participating in

the study. The Investigator agrees not to allow the study drug to be administered from, nor stored at, any site other than the study site agreed upon with the Sponsor.

See [Appendix 7](#) for detailed descriptions of dosing for the SUBOXONE sublingual film. Detailed instructions for the preparation and administration of RBP-6000 are in [Appendix 8](#).

If at an injection visit there is a safety concern with administration of RBP-6000, after discussion with the medical monitor or sponsor, dosing can be delayed up to one week. In the event this occurs, the subsequent doses will be delayed. There must be at least 26 days between injections of study medication.

All used syringe components will be disposed of into an appropriate secure biohazard container or per the SOPs at the study site.

All used IMP packaging (e.g., carton, foil pouch) will be retained at the study site until the CRA conducts a visit to perform reconciliation. After the reconciliation is completed, the used IMP packaging may then be disposed of per the SOPs at the study site.

Unused IMP and returned SUBOXONE sublingual film must be available for verification by the Sponsor's site monitor during on-site monitoring visits. The return of unused or used returned IMP for destruction will be documented on the drug return form.

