3.1 Sample Size Considerations

This study is designed to assess the long-term safety, tolerability, and clinical outcomes of RBP-6000 SC injections in subjects with opioid use disorder. Approximately 300 *de novo* subjects as well as approximately 300 roll-over subjects who completed the RB-US-13-0001 study will be enrolled into this long-term safety study. The planned number of subjects was designed to ensure at least 100 subjects reach 1 year of treatment with RBP-6000 (as advised in the ICH-E1A Guideline – The Extent of Population Exposure to Assess Clinical Safety: For Drugs Intended for Long-term Treatment of Non-Life-Threatening Conditions).

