3.3 Study Duration

The expected maximum duration of participation for *de novo* subjects is up to approximately 55 weeks consisting of up to a 7-day screening period, up to a 14-day SUBOXONE sublingual film Run-In, up to a 48-week open-label treatment period, and a 4-week follow-up and transition period when subjects will receive the same dose of SUBOXONE that they received at Day -1 and their ongoing treatment options will be reviewed.

The expected maximum duration of participation for roll-over subjects is up to approximately 31 weeks, consisting of up to a 7-day screening period, up to a 14-day SUBOXONE sublingual film Run-In, a 24-week open-label treatment period, and a 4-week follow-up and transition period when they will receive the same dose of SUBOXONE that they received at Day -1 and their ongoing treatment options will be reviewed.

If at least 100 subjects reach 1 year of exposure to RBP-6000 in RB-US-13-0001 and RB-US-13-0003, the study may be stopped early, and all remaining subjects will complete EOS procedures and enter the SUBOXONE Transition Period/Safety Follow-up.

Subjects who receive at least 1 dose of RBP-6000 and discontinue the trial for any reason will be required to complete the Early Termination (ET) visit.

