Appendix 3 List of Post-text Tables, Figures, Listings, and Supportive SAS Output Appendices

The TFL shells and table of contents for this study are provided in a separate document titled “Indivior 130003 SAP TFLs Version 3.0”.

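### Exposure is counted in this study alone and roll-over subjects form one column with a Day 1 baseline, so part of the one-year count and some early, lasting effects are hard to read in the final tables

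*SAP*

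**What the plan says.** **Columns.** SAP 9.0: "Unless otherwise stated, summaries will be presented by subject type (de novo or roll-over and total". SAP 5.0 gives subject type two levels and does not divide roll-over subjects by their RB-US-13-0001 treatment. The further subgroups in SAP 9.3 concern opioid use at screening and during run-in.

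**Exposure.** SAP 9.4: "Exposure will be derived as date of first RBP-6000 injection on the RB-US-13-0003 study", ending 28 days after the last injection in this study. SAP 5.0 uses the same end point: "treatment stop date is defined as date of last RBP-6000 injection + 28 days". The rows are described as "The duration of exposure in the 0-<4 weeks through 48 – <52 weeks".

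**One-year count.** SAP 3.3: "If at least 100 subjects reach 1 year of exposure to RBP-6000 in RB-US-13-0001 and RB-US-13-0003, the study may be stopped early". SAP 3.1: "The planned number of subjects was designed to ensure at least 100 subjects reach 1 year of treatment with RBP-6000", without saying whether that target spans two studies. Neither document converts one year into weeks.

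**Baseline.** For every subject it is the last value before the Day 1 injection of this study (SAP 5.0; Protocol 9.5.1).

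**Table shells.** SAP Appendix 3: "The TFL shells and table of contents for this study are provided in a separate document". That document was not available for this review.

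**The concern.** De novo subjects never took part in RB-US-13-0001. Naming that study in the early-stop sentence therefore has a meaning only if roll-over exposure is added up over both studies. SAP 9.4 does not add it up, so a subject with 12 RBP-6000 injections in all would be tabulated at about 24 weeks.

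Roll-over subjects are also of two kinds. Former placebo subjects (Protocol 3.1) are in their first six months on RBP-6000. Completers of the two RBP-6000 arms (Protocol 1.5 and 4.2 B) are in about months 7 to 12, and their Day 1 value is taken with depot drug still present. A change that arose in RB-US-13-0001 and persisted is already in their baseline, so a change-from-baseline table cannot show it.

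The primary objective is long-term safety. At stake is how well the final tables show one-year exposure and the time course of effects. The study is descriptive, so no error rate is involved.

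**Working it through.** **1. The plan's own figures.** SAP 3.3 gives treatment periods of 24 weeks (roll-over) and 48 weeks (de novo). Scheduled last injections are on Days 141 and 309 (Protocol Appendices 3 and 5). The target of 100 one-year subjects cannot be reproduced: Protocol 9.2 states that there was no formal calculation, and no retention rate is given.

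**2. Exposure under the SAP rule.** Weeks = (stop − start + 1)/7, with start = Day 1 and stop = last injection + 28 days. This reduces to (last injection day + 28)/7. Intervals run from 26 to 32 days (Protocol 5.3), and for a safety concern "dosing can be delayed up to one week" (Protocol 6.8).

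| Case | Injections | Interval, days | Last injection day | Weeks |
|---|---|---|---|---|
| Roll-over, on schedule | 6 | 28 | 1 + 5×28 = 141 | 169/7 = 24.1 |
| Roll-over, longest in window | 6 | 32 | 1 + 5×32 = 161 | 189/7 = 27.0 |
| Roll-over, each interval also a week late | 6 | 39 | 1 + 5×39 = 196 | 224/7 = 32.0 |
| De novo, shortest in window | 12 | 26 | 1 + 11×26 = 287 | 315/7 = 45.0 |
| De novo, on schedule | 12 | 28 | 1 + 11×28 = 309 | 337/7 = 48.1 |
| De novo, longest in window | 12 | 32 | 1 + 11×32 = 353 | 381/7 = 54.4 |

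The on-schedule results match the plan's 24 and 48 weeks. No roll-over subject can reach the 48-week row. A de novo subject reaches 52 weeks (364 days) at a mean interval of (364 − 29)/11 = 30.5 days, inside the window, and then has no listed row.

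**3. Two-study exposure of a former RBP-6000 subject, on schedule.**
- Without the gap between studies: (169 + 169)/7 = 48.3 weeks.
- Shortest gap, 4 days: run-in starts on the day of the earlier end-of-study visit (Day 169), the criteria are met on the fourth day, and the injection follows the next day.
- Longest gap, 21 days: 7 days to start plus 14 days of run-in (Protocol 4.4 and 5.2.1.2).
- With the gap: (168 + 4 + 169)/7 = 48.7 to (168 + 21 + 169)/7 = 51.1 weeks.

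On schedule, then, nobody reaches 52 weeks in either group. Whether the one-year count is large or close to nil depends on a definition that neither document gives.

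**4. Is the Day 1 baseline on-depot?** Protocol 1.4.2 gives single-dose half-lives of 1078 h (44.9 days) at 50 mg to 1573 h (65.5 days) at 200 mg. Taking these as a guide, the share of the Day 169 level left at Day 1 is 0.5^(21/44.9) = 0.72 to 0.5^(4/65.5) = 0.96. So it is.

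**5. Which tables this reaches.**
- Affected: mean change from baseline, the >30/>60 msec ECG table (SAP 9.6.4.1), and the worst-result laboratory shift, which is limited to subjects with a normal baseline (SAP 9.6.2). By-visit Total is affected through Week 25; later visits hold de novo subjects only.
- Not affected in this way: the de novo column, by-visit actual values, the tables in multiples of the upper limit of normal (SAP 9.6.2.2), the baseline-to-last laboratory shift, and the listing of all adverse events.
- Adverse events ongoing at roll-over are not treatment-emergent, but one that changes in severity is captured as a new event (SAP 5.0).

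**6. Size.** Let f be the share of roll-over subjects formerly on RBP-6000, and g the part of a mean change acquired before Day 1. The roll-over column then shows 1 − f·g of the change, and Total shows 1 − f·g/2 (300 and 300 subjects, no dropout). The documents give neither f nor g. Purely as illustration, f from 0.25 to 0.90 and g from 0.5 to 1 give 10% to 88% for roll-over and 55% to 94% for Total. A range that wide is not evidence of size. The formula does not apply to the ECG threshold counts.

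**The case against.** **The early stop.** A reader might infer that the stopping decision is left without the count it needs. The documents do not support that. SAP 1.0 says this version serves final reporting, whereas stopping early is discretionary and would be decided before final tables exist.

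**The sample-size target.** A reader might also infer that the target of 100 cannot be checked at all. SAP 3.1 does not say that it is a two-study count, and de novo subjects alone could meet it with 100/300 = 33.3% reaching one year. If one year means about 48 weeks, their part can be read from the number completing (defined as 12 doses plus the final visit, SAP 5.0 and 9.1), the dose-count summary and the exposure rows (SAP 9.4). A subject beyond 52 weeks can be found in the injection listing. All of this stands. What remains is the former-RBP-6000 part, the missing definition and the missing row.

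**Unseen shells.** They could contain a two-study table, so it cannot be said that none is planned. But the SAP text defines no derivation for one, and SAP 8.1 names no transfer of RB-US-13-0001 data.

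**Baseline.** Day 1 was set in the protocol and properly answers what changed during this study. All subjects, de novo included, reach it on SUBOXONE, so no column has a buprenorphine-free baseline. This stands, and it is why the current tables should stay. It does not remove the difference between up to 14 days of run-in and about six months of depot treatment.

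**Safeguards.** The de novo column gives up to 12 months against a pre-depot baseline, and the absolute-value tables still show persisting abnormalities. A reader might infer that lasting harm would be hidden; with these outputs in place, that goes too far.

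**Conclusion.** The concern holds as a cheap improvement, with one error in the exposure rows.

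- **Exposure.** This follows from the documents by arithmetic. Roll-over subjects show about 24 weeks and never more than 32.0, whatever they received before. In-window de novo subjects can reach 54.4 weeks, past the last listed row. The former-RBP-6000 part of the one-year count is in no table that the SAP text describes, subject to the unseen shells. The consequence is confined to final reporting of one-year exposure.
- **Column and baseline.** The direction is clear: the three affected kinds of table can understate early, lasting effects in the roll-over column and in Total. This assumes that such effects exist and that some roll-over subjects had received RBP-6000. The size cannot be computed, and no percentage should be quoted as a finding.

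**What to change.** Keep the current tables and add:

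1. A table of cumulative RBP-6000 exposure over both studies, with the number reaching one year. State how many weeks or injections count as one year and whether the run-in gap is included. Add a row for 52 weeks or more.
2. A split of the roll-over column by RB-US-13-0001 treatment (placebo or RBP-6000) in the key safety tables.
3. As a supplement for former RBP-6000 subjects, the change, shift and QTc-outlier tables against their baseline before the first RB-US-13-0001 dose.

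**Cost.** A merge of RB-US-13-0001 treatment codes, dosing dates and baseline values, possible only once that study is unblinded (no date is given). Roll-over subjects keep their numbers (Protocol 5.4), so records can be linked, but the transfer must be added to SAP 8.1. There will be more output and smaller subgroups. No choice of baseline recovers subjects kept out of this study because of earlier adverse events (Protocol 4.3 B).
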